# 5.11.5.3 Sensitivity and Supportive Analyses for the Key Secondary Efficacy Endpoints

Sensitivity analyses:

The main statistical analysis assumes that the treatment effect is constant over the standard explanatory variables. Additional sensitivity analyses will investigate whether the treatment effect varies with the explanatory variables: including, but not limited to, subgroup analyses by biochemical control status at baseline, fludrocortisone use at baseline, region or country as appropriate and pre-treatment corticosteroid. Separate summary tables will be presented for each subgroup and a measure of treatment-by-subgroup interaction together with confidence interval

and P-value provided. Forest plots will additionally be presented to provide a visual comparison of the differences in treatment effect between subgroups.

Supportive analysis: The main statistical analysis for each of the key secondary endpoints will additionally be performed on the EES.

# 5.11.6 Other Secondary Efficacy Endpoints

# 5.11.6.1 Standard Explanatory Variables for Other Secondary Efficacy Endpoints

The standard explanatory variables are (1) whether or not the participant was in biochemical control at baseline, (2) whether or not the participant was receiving fludrocortisone at baseline and (3) their interaction. Randomization of participants to treatment arm is stratified by fludrocortisone treatment and the analyses will include the stratification of biochemical control.

Analyses will be stratified or adjusted, as appropriate, on the basis of (i) the participant's fludrocortisone replacement status at baseline (requires fludrocortisone or does not require fludrocortisone) and (ii) whether they are in biochemical control at baseline or not (based on the androgen results from the baseline visit [Visit 2]). Participants with 17-OHP equal to or below the upper limit for optimal control at 08:00 hours and A4 equal to or below the upper limit of the reference range will be classified as 'in biochemical control'. Participants with 17-OHP above the upper limit for optimal control and/or A4 above the upper limit of the reference range will be classified as 'not in biochemical control'.

Considerations for model adjustments specified in Section 5.11.4 also apply to the analysis of other secondary efficacy endpoints.

# 5.11.6.2 Standard Methodology for Comparisons of Other Secondary Efficacy Endpoints

Unless otherwise stated, continuous outcome variables will be compared between treatment arms using analysis of covariance (ANCOVA) adjusting for the standard explanatory variables. Unless otherwise stated, a treatment policy approach will be assumed for all ICEs, with no imputation of missing data. If a non-normal distribution is anticipated or observed, then consideration will be given to using a logarithmic transformation or a non-parametric analysis. Analyses of change from baseline will always include the baseline value as a covariate. Example code is provided in Section 11.4.

Unless otherwise stated, binary outcome variables will be compared between treatment arms using logistic regression adjusted for the standard explanatory variables. Unless otherwise stated, a treatment policy approach will be assumed for all ICEs, with non-responder imputation of

missing data. The procedure described by Ge et al. (2011) will be used to estimate the standard error and resulting confidence interval around the covariate adjusted difference in proportions

Outcome Variables	Outline Analyses
Whether or not the participant is a biochemical	The same analysis will be used as for the primary
responder at 4, 10 and 16 weeks after	estimand of the primary outcome variable (except
randomization.	that at 4 weeks there has been no opportunity for a
	dose titration so the condition on dose is not used).
Whether or not the participant is a dose	The same analysis will be used as for the primary
responder at 10 and 16 weeks after	estimand of the first key secondary outcome
randomization.	variable.
Total daily dose at 10 and 16 weeks after	The same analysis will be used as for the primary
randomization.	estimand of the second key secondary outcome variable.
Whether or not the participant is in biochemical	The same analysis will be used as for the primary
control (provided total daily dose is not greater	estimand of the primary outcome variable.
than 30mg) at 4, 10, 16 and 28 weeks after	
randomization.	
The difference in range as calculated as the	Standard methodology for comparisons.
difference between the 08:00 and 13:00 17-OHP	
levels at 4, 10, 16 and 28 weeks after	
The difference in range as calculated as the	Standard methodology for comparisons.
difference between the 08:00 and 13:00 A4	
revers at 4, 10, 10 and 28 weeks after	
The mean of the 08:00 and 13:00 levels for each	Standard methodology for comparisons
androgen at 4, 10, 16 and 28 weeks after	Standard methodology for comparisons.
randomization	
The total daily elucocorticoid dose at 4 10 16	Standard methodology for comparisons Total
and 28 weeks after randomization.	glucocorticoid daily dose will be calculated as mean
	total daily dose of study medication and other
	additional glucocorticoids over the time interval
	since previous visit. Additionally, the mean total
	daily dose by treatment will be calculated for
	participants in and not in biochemical control at the
	end of study visit.

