9.4.2.4. Other Secondary Efficacy Analyses

Outcome Variables	Outline Analyses
Whether or not the participant is a biochemical responder at 4, 10, and 16 weeks after randomization.	The same analysis will be used as for the primary outcome variable (except that at 4 weeks there has been no opportunity for a dose titration so the condition on dose is not used).
Whether or not the participant is a dose responder at 10 and 16 weeks after randomization.	The same analysis will be used as for the first key secondary outcome variable.
Total daily dose at 10 and 16 weeks after randomization.	The same analysis will be used as for the second key secondary outcome variable.
Whether or not the participant is in biochemical control (provided total daily dose is not greater than 30 mg) at 4, 10, 16, and 28 weeks after randomization.	The same analysis will be used as for the primary outcome variable.
The difference in range as calculated as the difference between the 08:00 and 13:00 17-OHP	Standard methodology for comparisons.

levels at 4, 10, 16, and 28 weeks after randomization.	
The difference in range as calculated as the difference between the 08:00 and 13:00 A4 levels at 4, 10, 16, and 28 weeks after randomization.	Standard methodology for comparisons.
The mean of the 08:00 and 13:00 levels for each androgen at 4, 10, 16, and 28 weeks after randomization.	Standard methodology for comparisons.
The total daily glucocorticoid dose at 4, 10, 16, and 28 weeks after randomization.	Standard methodology for comparisons. Additionally, the mean total daily dose by treatment will be calculated for participants in and not in biochemical control at the EOS visit.
The change from baseline to 4, 10, 16, and 28 weeks of randomized treatment in menstrual regularity	Standard methodology for comparisons (only in pre-menopausal women without hysterectomy and not using hormonal contraception)
The change from baseline to 4, 10, 16, and 28 weeks of randomized treatment in LH levels	Standard methodology for comparisons (men only)
The change from baseline to 28 weeks of randomized treatment in size of TART	Standard methodology for comparisons (men only)
The change from baseline to 28 weeks of randomized treatment in sperm count	Standard methodology for comparisons (men only)
The change from baseline to 4, 10, 16, and 28 weeks of randomized treatment in objective hirsutism using the Ferriman-Gallwey score	Standard methodology for comparisons (women only)

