• To compare Chronocort to IRHC in terms of biochemical control at 4, 10, 16 and 28 weeks after randomization.	• The outcome variables whether or not the participant is in biochemical control (provided total daily dose is not more than 30 mg) at 08:00 hours at 4, 10, 16 and 28 weeks after randomization are compared between treatment arms by calculating the difference in proportion of participants in control.
• To compare Chronocort to IRHC in terms of the impact on 17-OHP range.	• The difference in range as calculated as the difference between the 08:00 and 13:00 measurements of 17-OHP levels at 4, 10, 16 and 28 weeks after randomization and their changes from baseline will be summarized and compared between treatment arms.

• To compare Chronocort to IRHC in terms of the impact on A4 range.	• The difference in range as calculated as the difference between the 08:00 and 13:00 measurements of A4 levels at 4, 10, 16 and 28 weeks after randomization and their changes from baseline will be summarized and compared between treatment arms.
• To compare Chronocort to IRHC in terms of the impact on mean 17-OHP and A4.	• The mean of the 08:00 and 13:00 measurements of 17-OHP levels and A4 levels at 4, 10, 16 and 28 weeks after randomization and their changes from baseline will be summarized and compared between treatment arms.
• To compare Chronocort to IRHC in terms of the impact on glucocorticoid dose.	
 
The total daily glucocorticoid dose at 4, 10, 16 and 28 weeks after randomization will be summarized and compared between treatment arms.
 
The relationship between daily glucocorticoid dose and biochemical control at 28 weeks after randomization will be explored.
 

• To compare Chronocort to IRHC in terms of changes in menstrual regularity.	• The change from baseline to 4, 10, 16 and 28 weeks of randomized treatment in menstrual regularity (only in pre-menopausal women without hysterectomy and not using hormonal contraception) will be summarized and compared between treatment arms.
• To compare Chronocort to IRHC in terms of the impact on luteinizing hormone (LH) levels.	• The change from baseline to 4, 10, 16 and 28 weeks of randomized treatment in LH levels (men only) will be summarized and compared between treatment arms.

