# **3** SAMPLE SIZE

Sufficient participants will be screened to achieve approximately 50 participants randomly assigned to either Chronocort or IRHC (25 participants per treatment arm, regardless of baseline strata), or until a cut-off date of 30 April 2023, whichever is reached first. Individual study sites should not randomize more than 8 participants without first consulting the Sponsor. A sample size of 25 participants per treatment arm will provide at least 80% power to demonstrate non-inferiority of Chronocort to IRHC when the biochemical response rate in the IRHC arm is 40%, the non-inferiority margin is 15%, and the biochemical response rate in the Chronocort arm is 68% using a 1-sided continuity corrected z-test with unpooled variance and a 1-sided alpha of 2.5%. Sample size is calculated using PASS 2022 (v22.0.3).

Note: Basing the sample size calculation on a continuity corrected z-test provides a conservative estimate of sample size relative to the test, based on a logistic model adjusted for stratification factors, which will actually be used.

**Note:** Post-hoc analysis of study DIUR-005 showed that ~40% of participants receiving the control treatment (that is: their pre-randomization treatment) would have been down-titrated by the proposed rules for the current study at four weeks after randomization. Estimating therefore the response rate for the IRHC as 40% and expecting that no participants withdrawn completely from hydrocortisone treatment would qualify for down-titration, the estimated treatment benefit of IRHC is a gain in response rate of 40%. Setting the non-inferiority margin as minus 15% thus retains five eighths of the anticipated treatment benefit of IRHC.

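### The mean 17-OHP and mean A4 endpoints have two planned comparisons with different covariates, no stated main one, and no fixed scale

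*SAP*

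**What the plan says.** - **Outcome in the analysis tables.** Protocol 9.4.2.4 lists "The mean of the 08:00 and 13:00 levels for each androgen at 4, 10, 16, and 28 weeks after randomization" under the standard methodology. The corresponding row in SAP 5.11.6.3 does the same. Neither row mentions change from baseline.
- **Outcome in the objectives.** SAP Section 2 starts from "The mean of the 08:00 and 13:00 measurements of 17-OHP levels and A4 levels" at the same four visits, but adds their changes from baseline and says that both are compared between arms. Protocol Sections 1.1 and 3 agree with this.
- **Model.** SAP 5.11.6.2: "continuous outcome variables will be compared between treatment arms using analysis of covariance (ANCOVA) adjusting for the standard explanatory variables". SAP 5.11.6.1 defines those variables as baseline biochemical control (yes/no), fludrocortisone use (yes/no) and their interaction.
- **Baseline rule.** SAP 5.11.6.2: "Analyses of change from baseline will always include the baseline value as a covariate". Nothing equivalent is said for levels.
- **Baseline availability.** SAP 5.2.2 already defines the Visit 2 value as baseline for the average of the two daily samples.
- **Scale.** If non-normality is anticipated or observed, "consideration will be given to using a logarithmic transformation or a non-parametric analysis".
- **Status.** SAP 5.11.8 treats these endpoints as descriptive, without multiplicity control.

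**The concern.** Other rows of the same table (LH, weight, HbA1c, quality of life) are worded as change, so the baseline rule reaches them. The androgen means are worded as levels, so read literally it does not. The level model then knows a participant's starting androgen only through a yes/no control status. That status uses the 08:00 values alone and combines both androgens.

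Two things are at stake. First, the level and change comparisons can give different answers to the same question, with no rule on which to report as the result. Second, the scale may be chosen after the data have been seen. These means are the direct continuous measure of androgen control, which is the subject of the trial's rationale, and with about 25 participants per arm a chance baseline imbalance can carry into the level estimate.

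**Working it through.** **1. The plan's own figure.** The documents state no power or precision for the androgen means. The only figure is for the primary endpoint: "A sample size of 25 participants per treatment arm will provide at least 80% power". With rates of 40% and 68%, a 15-point margin, n = 25 and a continuity correction of 1/25 = 0.04:

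SE = √(0.40×0.60/25 + 0.68×0.32/25) = 0.1353

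Power = Φ((0.28 + 0.15 − 0.04)/0.1353 − 1.96) = 82.2%

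The stated figure reproduces. It says nothing about the androgen means.

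**2. Where the two comparisons differ.** On one scale, ANCOVA of change with baseline as covariate gives the same treatment estimate and standard error as ANCOVA of the level with that covariate. So the planned level and change comparisons differ only because the level model omits the baseline value.

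**3. Precision lost in the level comparison.** Let ρ be the baseline-to-visit correlation on the log scale and p the proportion in control at baseline. Relative residual variance is:

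- binary status only: 1 − ρ²·φ(c)²/(p(1−p)), where c is the normal quantile of p
- continuous baseline: 1 − ρ²

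The documents give neither ρ nor p. Assuming p = 0.5, φ(0)²/0.25 = 0.637.

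| ρ | binary only | continuous | CI narrower by | effective n per arm (from 25) |
|---|---|---|---|---|
| 0.3 | 0.943 | 0.910 | 2% | 25.9 |
| 0.5 | 0.841 | 0.750 | 6% | 28.0 |
| 0.7 | 0.688 | 0.510 | 14% | 33.7 |
| 0.8 | 0.593 | 0.360 | 22% | 41.2 |

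Simulation with 17-OHP medians of 1200 to 3000 ng/dL and log-SD 1.0 to 1.4 gives 4 to 18% for ρ of 0.5 to 0.7, and about 1% at 0.3.

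**4. Scale and baseline separated.** Simulated two-sided 5% power, 25 per arm, 3,000 trials per setting. Assumed: lognormal values, true ratio 0.5, half in control at baseline, 80% on fludrocortisone. All four models include the standard factors.

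| log-SD | ρ | raw, no baseline value | raw + raw baseline | log, no baseline value | log + log baseline |
|---|---|---|---|---|---|
| 1.0 | 0.3 | 46.7% | 46.7% | 66.6% | 67.6% |
| 1.0 | 0.5 | 48.9% | 50.5% | 70.8% | 74.0% |
| 1.0 | 0.7 | 54.5% | 65.1% | 80.4% | 89.4% |
| 1.5 | 0.3 | 16.6% | 16.4% | 35.5% | 35.7% |
| 1.5 | 0.5 | 19.3% | 20.0% | 41.4% | 44.6% |
| 1.5 | 0.7 | 19.1% | 24.6% | 47.4% | 58.0% |

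With no true effect (log-SD 1.0, ρ = 0.5), rejection rates were 4.4 to 5.6%.

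At log-SD 1.0 and ρ = 0.5, the scale adds 70.8 − 48.9 = 21.9 points and the log baseline a further 74.0 − 70.8 = 3.2. At ρ = 0.7 the figures are 25.9 and 9.0. Most of the gain is the scale.

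**5. Can the two planned comparisons disagree?** On the raw scale (ratio 0.5, log-SD 1.0 to 1.4, ρ 0.5 to 0.7, medians as in step 3), the tests with and without the baseline value differed on significance in 8 to 25% of simulated trials.

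**The case against.** A reader might infer that the plan throws away the baseline androgen data. The documents do not support that. Section 2 commits to comparing changes, the covariate rule then brings in the participant's own baseline, and SAP 5.2.2 defines it. On a common scale nothing is lost in that comparison.

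A reader might also infer that the plan fixes a raw-scale analysis. It does not. The rule allows a log or non-parametric analysis as soon as skew is anticipated, so raw-scale ANCOVA is the least favourable outcome of the rule rather than its content. The simulation includes no non-parametric option.

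Nor can skew be read off the 300 ng/dL titration limit and the 1200 ng/dL control limit for 17-OHP. Two decision thresholds say nothing about the shape of a distribution, and they do not concern A4.

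Finally, the example code in SAP 11.4 is not visible in the available copy and might settle the covariates. The SAP's label ANCOVA, where Protocol 9.4.2 says ANOVA, does not settle it.

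All of this stands and limits the point. It does not remove the mismatch between Section 2 and the analysis table, the lack of a named main comparison, or the open choice of scale. The change comparison, if run on raw values, also does not recover what the log scale gives (50.5% against 74.0% at log-SD 1.0 and ρ = 0.5).

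**Conclusion.** The point holds as an inconsistency plus a modest, avoidable loss in one of two comparisons. As worded, the level comparison omits the participant's own baseline and the change comparison includes it, with no order between them and no fixed scale.

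The loss attributable to the missing baseline is about 4 to 18% of the log-scale standard error for ρ of 0.5 to 0.7, and about 1% at 0.3. Power differences of 20 points or more appear only when a raw-scale analysis is set against a log-scale one, and they rest on assumed lognormal spread and a true halving. The correlations, SDs, medians, proportion in control, fludrocortisone share and effect are all assumptions, since the documents give none.

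The endpoints are descriptive, so neither the primary nor a key secondary conclusion is affected. The change is worth making because it costs almost nothing.

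**What to change.** Align SAP Section 2 with the table in SAP 5.11.6.3. In 5.11.6.2 and 5.11.6.3, name one comparison per androgen per visit before unblinding:

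- **Outcome:** log of the mean of the 08:00 and 13:00 values.
- **Model:** ANCOVA with treatment, the log Visit 2 mean of the same androgen, and the standard explanatory variables.
- **Report:** ratio of geometric means with 95% CI.
- **Raw levels and changes:** kept as description, without a second between-arm test.

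Check that the example code in SAP 11.4 matches, and carry the wording into the equivalent rows of Protocol 9.4.2.4 or list the difference in SAP Section 8.

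Cost: SAP wording and a small programming change, with no new data. The downside is that the effect is reported as a ratio rather than in ng/dL, which the descriptive raw summaries partly offset.

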5.11.6.3 Analyses of Other Secondary Efficacy Endpoints

Outcome Variables	Outline Analyses
The change from baseline to 4, 10, 16 and 28	Standard methodology for comparisons (only in
weeks of randomized treatment in menstrual	pre-menopausal women without hysterectomy and
regularity	not using hormonal contraception).
	
 
Note, post treatment menstrual regularity will be derived from the menstrual cycle log using the following definitions:
 
Oligomenorrhoea is defined as fewer than 9 menstrual cycles per year or cycle length >35 days
 
Amenorrhoea is defined as absent menses for ≥3 months.
 

The change from baseline to 4, 10, 16 and 28 weeks of randomized treatment in LH levels	Standard methodology for comparisons (men only)
The change from baseline to 28 weeks of	Descriptive statistics only (men with TART at
randomized treatment in size of TART	baseline). Percentage change from baseline will be summarized.
The change from baseline to 28 weeks of	Standard methodology for comparisons (men only)
randomized treatment in sperm count	
The change from baseline to 4, 10, 16 and 28	Standard methodology for comparisons (women
weeks of randomized treatment in objective	only)
hirsutism using the Ferriman-Gallwey score	
The change from baseline to 4, 10, 16 and 28	Standard methodology for comparisons (women
weeks of randomized treatment in objective	only)
scale	
The change from screening to 4, 10, 16 and 28	Standard methodology for comparisons
weeks of randomized treatment in HbA1c levels	Standard methodology for comparisons
The change from baseline to 4, 10, 16 and 28	Standard methodology for comparisons
weeks of randomized treatment in waist	Sumara memodology for companyons
circumference	
The change from baseline to 4, 10, 16 and 28	Standard methodology for comparisons
weeks of randomized treatment in body weight	57 1
The change from baseline to 4, 10, 16 and 28	Standard methodology for comparisons
weeks of randomized treatment in QoL using	
the self-completed SF-36 ® total score and the	
sub-domain of vitality	
The change from baseline to 4, 10, 16 and 28	Standard methodology for comparisons
weeks of randomized treatment in QoL using	
the MAF	
The change from baseline to weeks 4, 10, 16	Standard methodology for comparisons (women
and 28 in subjective hirsufism and acne using a	only).
weeks of randomized treatment in QoL using the MAF The change from baseline to weeks 4, 10, 16 and 28 in subjective hirsutism and acne using a participant-reported VAS.	Standard methodology for comparisons (women only).

Outcome Variables	Outline Analyses
The change from baseline to weeks 4, 10, 16	Standard methodology for comparisons.
and 28 in QoL using the EQ-5D-5L ™ .	

# 5.11.8 Multiplicity

The results of the key secondary analysis (dose response) will only be considered substantive if the primary estimand of the primary analysis demonstrates non-inferiority, otherwise the results will be considered indicative. Similarly, the analysis of the second key secondary efficacy endpoint (total daily dose) will be considered substantive if the primary estimand of the primary efficacy endpoint and key first secondary endpoint demonstrate success.

All other analyses of secondary endpoints, analyses of exploratory endpoints and sensitivity and supportive analyses will be considered as descriptive evidence of efficacy and will be analyzed without any procedures to account for multiple comparisons.

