1.1. Synopsis

Protocol Title: A Randomized, Double-Blind, Active-Controlled, Phase 3 Study of Chronocort Compared with Immediate-Release Hydrocortisone Replacement Therapy in Participants Aged 16 Years and Over with Congenital Adrenal Hyperplasia

Study Name: CONnECT

Short Title: Double-blind comparison of Chronocort versus standard hydrocortisone replacement therapy in participants aged 16 years and over with congenital adrenal hyperplasia

Rationale: Congenital adrenal hyperplasia (CAH) is most commonly caused by 21-hydroxylase deficiency that results in cortisol deficiency and androgen excess, with or without aldosterone deficiency. Patients are currently treated with glucocorticoid replacement therapy, but immediate-release formulations fail to replicate the natural cortisol circadian rhythm, and patients often struggle to take an afternoon dose, resulting in patients being poorly controlled. Chronocort is a newly developed modified release oral formulation of hydrocortisone, and it is designed to closely replicate the normal serum levels of the endogenous cortisol circadian rhythm, offering the prospect of an improved treatment outcome and a novel treatment paradigm. The proposed study will evaluate whether a twice daily dosing regimen of Chronocort, with two-thirds of the total daily dose given at night and one-third in the morning (the ‘toothbrush regimen’), which can more closely replicate circadian cortisol levels, will improve control of adrenal androgen production (as measured by 17-hydroxyprogesterone [17-OHP] and androstenedione [A4] concentrations) compared to a similarly titrated regimen of twice daily immediate-release hydrocortisone replacement therapy (IRHC) in conditions broadly resembling routine clinical practice.

Objectives, Outcome Variables, and Analyses

[figure not shown]
Objectives	Outcome Variable and Analyses Supporting the Objectives

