#### **1** INTRODUCTION

This document details the planned statistical analyses for the Diurnal, protocol "DIUR-014" study titled "A Randomized, Double-Blind, Active-Controlled Phase 3 Study of Chronocort Compared with Immediate-Release Hydrocortisone Replacement Therapy in Participants Aged 16 Years and Over with Congenital Adrenal Hyperplasia".

The proposed analyses are based on the contents of the final version 7.0 of the protocol (dated 30 October 2023).

Congenital adrenal hyperplasia (CAH) is most commonly caused by 21-hydroxylase deficiency that results in cortisol deficiency, with or without aldosterone deficiency, and androgen excess. Patients are currently treated with glucocorticoid replacement therapy, but immediate release formulations fail to replicate the natural cortisol circadian rhythm, and patients often struggle to take a midday dose, resulting in patients being poorly controlled. Chronocort® is a newly developed modified release oral formulation of hydrocortisone, and it is designed to closely replicate the normal serum levels of the endogenous cortisol circadian rhythm, offering the prospect of an improved treatment outcome and a novel treatment paradigm.

The proposed study will evaluate whether a twice daily dosing regimen of Chronocort®, with two-thirds of the total daily dose given at night and one-third in the morning (which can more closely replicate circadian cortisol levels) will improve control of adrenal androgen production (as measured by 17-hydroxyprogesterone [17-OHP] and androstenedione [A4]) compared to a similarly titrated regimen of twice daily immediate release hydrocortisone replacement therapy (IRHC) in conditions broadly resembling routine clinical practice. The study design is presented in the schema in Figure 1.

This is a randomized, double blind, active controlled, titrated, parallel arm, multicenter study. After a 4-week run-in period, participants will be randomized on a 1:1 basis to either Chronocort® or IRHC (Cortef®, Pfizer Inc.).

Version 1.0 of the statistical analysis plan (SAP) was developed and finalized before the first participant is screened and contained a full description of the statistical methods to be used. Versions 2.0 and 3.0 have updated the SAP in line with the subsequent protocol amendments.

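### The confirmatory sequence contains no superiority reading of biochemical response; a fourth and last step would add one at no alpha cost, though its benefit is limited

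*SAP*

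**What the plan says.** The rationale in the Protocol synopsis (1.1) asks whether the Chronocort regimen "will improve control of adrenal androgen production" compared with a similarly titrated IRHC regimen, and SAP Section 1 repeats it. The formal primary objective in both documents is worded as a comparison.

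SAP Section 3 plans on an IRHC rate of 40%, and there "the non-inferiority margin is 15%, and the biochemical response rate in the Chronocort arm is 68"%. The planned difference is therefore +28 points.

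The confirmatory sequence has three steps, set out in SAP 5.11.1.1 to 5.11.1.3 and Protocol 9.1:

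1. Non-inferiority on biochemical response: 95% CI wholly above minus 15 points.
2. Superiority on dose response: 95% CI wholly above zero.
3. Superiority on mean total daily dose: 95% CI wholly below zero.

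SAP 5.11.8 governs the order: "The results of the key secondary analysis (dose response) will only be considered substantive if the primary estimand of the primary analysis demonstrates non-inferiority". Step 3 counts only if steps 1 and 2 succeed. The overview table of efficacy analyses (SAP 5.11.1.4) makes any other analysis of the primary outcome supplementary, with indicative p-values. Biochemical control at week 28 at a dose of not more than 30 mg is an other secondary endpoint, which 5.11.8 treats as descriptive.

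**The concern.** The sponsor asks about improvement and plans on a 28-point gain, yet the strongest confirmatory statement available about biochemical response is that it is not worse by 15 points or more. If the CI for the primary endpoint lay wholly above zero, the plan would still support only non-inferiority on that endpoint. Because the same interval already carries this information, a trial that shows a clear gain would be unable to claim it for want of one pre-specified sentence.

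Dose superiority does not fully replace the missing claim. Protocol 4.4 (Endpoints) explains that every dose responder is a biochemical responder. The additional biochemical responders are participants who were uncontrolled at baseline and are controlled at week 28 on no more than 30 mg. Those still at 30 mg count in the primary endpoint but not in dose response.

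**Working it through.** **Inputs.** SAP Section 3: IRHC 40%, Chronocort 68%, margin 15 points, 25 per arm, "using a 1-sided continuity corrected z-test with unpooled variance and a 1-sided alpha of 2.5"%. Allocation is 1:1 (SAP Section 4).

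**The plan's own figure.** The unpooled standard error is SE = √(0.40×0.60/25 + 0.68×0.32/25) = 0.1353. The continuity correction is 1/25 = 0.04.

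Non-inferiority power = Φ[(0.28 + 0.15 − 0.04)/0.1353 − 1.96] = Φ(0.92) = 82.2%. The stated minimum of 80% is confirmed. Exact enumeration of the corrected test gives 79.8%.

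This power depends on the assumed gain. With equal true rates of 40% to 68% in both arms, the same corrected formula gives only about 12% to 13%.

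**Chance that the 95% CI on biochemical response excludes zero at the planned rates.** The same formula is used with a margin of zero.

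| Variant | Probability |
|---|---|
| Unpooled, continuity-corrected: Φ(0.24/0.1353 − 1.96) | 42.6% |
| Exact enumeration, corrected | 44.7% |
| Pooled, uncorrected | 51.1% |
| Unpooled, uncorrected: Φ(0.28/0.1353 − 1.96) | 54.4% |
| Exact enumeration, uncorrected | 56.5% |

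If the trial observed exactly its planned rates (17/25 against 10/25), the unadjusted interval would be 28 ± 1.96 × 13.53, or +1.5 to +54.5 points. That excludes zero.

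**Chance of an actual claim as the last step.** The claim also needs steps 2 and 3. The documents give no planning rate for dose response and no mean or SD for total daily dose, so this chance cannot be derived from them. To show the range, steps 1 and 2 were simulated at 68% against 40% with 25 per arm, uncorrected unpooled intervals, and dose responders nested within biochemical responders. The dose-responder rates are assumptions. Step 3 is left out and would lower every figure.

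| Assumed dose-responder rates, Chronocort v IRHC | Pass steps 1 and 2 and biochemical superiority |
|---|---|
| 30% v 30% | 3% |
| 40% v 30% | 12% |
| 50% v 30% | 31% |
| 58% v 30% | 47% |
| 68% v 40% (every responder a dose responder) | 56–57% |

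In the last row the new claim merely duplicates step 2. In the other rows, subtracting from 56.5% gives the chance that the CI excludes zero while dose superiority fails: about 44% at 40% v 30% (56.5 − 12) and about 10% at 58% v 30% (56.5 − 47). In those cases a last step yields no claim.

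**Is the uncovered group plausible?** Protocol 4.2 permits down-titration only if 17-OHP is below 300 ng/dL (with A4 also below its limit), while biochemical control allows 17-OHP up to 1200 ng/dL. A participant who moves from uncontrolled to, say, 800 ng/dL at both samples, with A4 in range, stays at 30 mg. That participant is a biochemical responder but not a dose responder.

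**The case against.** The best defence is that the sequence is coherent. The word improve stands in the rationale, while the objective and hypotheses are explicit about comparison and non-inferiority. Protocol 2.1 says the study should help separate the benefit of physiological delivery from the benefit of a lower dose, and non-inferior control followed by superiority on dose suits that purpose. Two of the three steps are superiority tests, and one of them requires biochemical control. Superiority on biochemical response with 80% power would need 46 to 56 per arm, against 25 planned, so leaving it out of the confirmatory set is defensible. Nor is the result hidden: SAP 5.11.4.1 requires the rates, their difference and the two-sided 95% CI to be presented.

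All of this stands, and it limits the point to a forgone claim. It does not remove the point, because a last step takes nothing from the existing tests however low its power.

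A second objection is that last placement fails where the claim is most wanted. If the gain comes mainly from participants controlled at 30 mg, dose superiority may fail and step four is never reached. That is also correct. Moving the step ahead of dose response would make that test depend on a step with only about 43% to 56% power, and testing both at full alpha after step 1 would not control the error rate.

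A reader might infer that the plan contradicts itself by pairing a 68% planning rate with a non-inferiority test. The documents do not support that: the planned power reproduces, and assuming a better treatment in a non-inferiority calculation is legitimate.

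**Conclusion.** The gap is real and modest. No part of the plan permits a confirmatory superiority statement on biochemical response, and dose superiority covers that claim only in part. Error control is sound and no existing claim is invalid.

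A reader might take 54% or 56% as the chance of gaining a claim. It is only the marginal chance that the CI excludes zero, about 43% to 56% across variants. The chance of reaching and passing a fourth step is lower and is not computable from the documents. The illustrative 12% to 47% rests on assumed dose-responder rates and ignores step 3.

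These calculations are unadjusted, whereas the planned analysis is a covariate-adjusted logistic model with multiple imputation. They also take 40% and 68% as already including withdrawals, which count as non-responses.

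**What to change.** Before unblinding, add a fourth and last step to SAP 5.11.8: if the first three steps succeed, superiority on biochemical response is declared when the lower limit of the same two-sided 95% CI from the primary analysis is above zero. Align SAP 5.11.1.1 and the overview table in 5.11.1.4, and list the change in Section 8 (and in Section 9, which records changes from SAP version 1.0).

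The cost is a few sentences. No alpha is spent, because a fixed sequence lets the last step use the full level, and no existing test depends on it. No new data or model are needed. The SAP should not present the step as a remedy for every case: it gives no claim when dose superiority or total-daily-dose superiority fails. If the sponsor does not want the step, one sentence should say that no superiority claim on biochemical response is intended.
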